
Aims 2 and 3 of the RCT will be completed simultaneously. The total targeted population for Aims 2 and 3 of the RCT are 240 enrolled patient/family dyads and a maximum of 60 randomized clinicians. To be considered "enrolled" for this study, a patient/family dyad must meet all eligibility criteria and receive a NEST score of > 15.

For aims 2 and 3, the study team will conduct a randomized clustered clinical trial. Randomization occurs at the ICU clinician level versus that of the patient/family level. Clinicians are identified as eligible if they are the current attending on service for the particular ICU. Clinicians are randomized to one of the two arms based on the following:

- 1. Gender (male/female)
- 2. Clinical Experience (<10 years vs > 10 years)
- 3. Discipline (medical vs. surgical)

Consented, enrolled clinicians are expected to complete the following survey(s):

• Baseline Demographics Survey (on the day of consent)

For those clinicians who are randomized to intervention, they will be required to complete the following:

- Review patient/family needs score and survey results within ICUconnect (at the completion of T1 by patient/family dyad)
- Schedule and conduct a family meeting (after T1 completion but before T2 completion)
- Review patient/family needs score and survey results within ICUconnect (at the completion of T2 by patient/family dyad)
- Complete the Clinician Survey via ICUconnect (after Family Meeting and completion of T1 and T2 by patient/family dyad).

Patient/family dyads will be identified at the time of ICU admission and approached for consent based on meeting study inclusion/exclusion criteria (see Selection of Subjects). Each patient/family member, if enrolled into the RCT will be asked to complete an ICUconnect profile and survey (T1). This survey is to be completed within 24 hours of consent to the study. Given that this study's intent is to address unmet needs, eligible participants must receive a NEST score of > 15 (see Study Eligibility Workflow).

- If a participant receives a NEST score of < 15 and they are assigned to a randomized intervention clinician, the participant is considered a screen failure.
- If a participant receives a NEST score of < 15 and is assigned to a randomized control clinician, the
 participant is considered a screen failure for the RCT but is allowed to continue participation within
 the ancillary study.

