The study consists of the following statuses for clinicians:

- Consented: an individual clinician who is on service at the time of the eligible patient/family dyad admission and has agreed to voluntarily consent to the study.
- Randomized: a clinician who has been randomized to one of the two study arms:
 - Interventin: a clinician wh receives the patient/family dyad T1 and T2 survey results, conducts a family meeting to discuss results, and completes a clinician survey post family meeting and survey results review.
 - Cntrol: a clinician wh neither receives patient/family dyad T1 and T2 surveys nor conducts a family meeting to discuss results.

Given the nature of the targeted population under study and that the goal of this study is to address unmet needs and racial disparities among ICU family members, we do not anticipate adverse events and /or serious adverse events. However, it is possible that the patient/family dyad could become distressed in an ICU setting, especially as the patient becomes more ill and/or dies. As a result, the study team will monitor, document and report suicidal ideation (SI) as an Adverse Event (AE). The monitoring of SI is operationalized by the participant responding to one of the survey questions (PHQ-9; #9: Thoughts that you would be better off dead or of hurting yourself in some way). An automated alert is triggered and an email is sent to the Principal Investigator, the Study Manager, and the Clinical Research Coordinators. The PI will be the primary responsible party for addressing the SI alert; however, the Study Manager may also serve in the PI's absence. Both are trained on the Columbia Suicide Severity Rating Scale (C-SSRS).

A serious adverse event (SAE) for this trial would include a suicide attempt. Again, given the nature of the targeted population under study, it is not unexpected that the patient would experience hospitalization and subsequent ICU admission (or even repeat hospitalization, if discharged), therefore, the study will not document and/or report hospitalizations and/or deaths for the patients. However, if the enrolled family member and/or clinician were to be hospitalized and/or pass away, the study team would consider this an SAE and would document and report appropriately.

All protocol defined AEs and SAEs will be reported to the appropriate agencies (NIH) and the institutional review board, as appropriate and in line with guidelines and policies.

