- -Study (R21 vs. ICUconnect intervention arm)
- -Gender
- -Trigger (present vs. absent)
- -Race
- -Age
- -Medical vs Surgical ICU (place of eligibility and recruitment)
- -NEST at T1 and T2 (responder vs. non-responder)
- -Technology confidence
- -Status (completed)

Families who meet the criteria listed above will be contacted via telephone and/or email and asked to participate in this portion of the project using the approved telephone and/or email consent template. Each individual will be asked to read, review, and sign/date an eConsent attesting to their willingness to participate.

As part of this aim, families who choose to participate will be asked to complete a 15 minute audio recorded interview in which the family member will be asked a series of questions pertaining to their loved one's hospitalization and ICU admission, the status of their loved one (alive or deceased), and then their overall experience related to their loved one's care in the ICU and their interactions with the clinical care team.

Selection of Subjects

• List inclusion/exclusion criteria and how subjects will be identified.

To identify eligible patient/family dyads for consent in both the RCT and the ancillary study, the study team will utilize the electronic medical record (EMR) known as EPIC for screening purposes. The study team will complete a daily review of the EMR, specifically reviewing each ICU unit and associated beds for patients who meet study criteria.

For both the RCT and the ancillary study, eligible participants are those patients who are at least at moderate risk of death or disability. In addition, while patients will not be excluded based on diagnosis, it is anticipated that most patients will predominantly be diagnosed with cardiorespiratory failure, stroke, trauma, and/or septic shock.

Eligible clinicians will be identified by the Principal and sub investigators. Clinicians must meet the criterion listed below. In addition, the selected clinician for consent and subsequent randomization should be scheduled to be on service at least 8 weeks per year (or the equivalent in terms of 12-hour shifts).

Inclusion Criteria (Patients, Pre-Consent)

- 1. ≥18 years of age
- 2. Patients must be on mechanical ventilation in a study ICU for ≥ 24 hours
 - a. For those patients whose mechanical ventilation is interrupted for <72 hours, they will remain eligible for study participation.

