 - b. If a patient is intubated on the day of eligibility but then subsequently extubated the same day, the patient remains eligible for the study as long as consent and T1 are completed within 8 hours of extubation.
- 3. Death must not be imminent (< 24 hours)

Inclusion Criteria (Family Members, Pre-Consent)

- 1. One family member per patient is eligible.
- 2. The family member must be \geq 18 years old.
- 3. The family member must be self-described as the individual (related or unrelated) who provides the most support and with whom the patient has a significant relationship.

Inclusion Criteria (Clinician, Pre-Consent)

1. Patients' bedside ICU attending physicians on the day of family consent are eligible.

Exclusion Criteria (Patients, Pre-Consent)

- 1. Patients who are admitted to an ICU at the index hospital >14 days will be ineligible for participation.
- 2. Patients who are on comfort care or are planned to undergo withdrawal of treatment within the following 48 hours of enrollment will be excluded.
- Prisoners
- 4. Patients who have no known family or surrogate.
- 5. Patients who are transferred to a non-study ICU or non-study clinician will be excluded if they are enrolled into the RCT only.

Exclusion Criteria (Family Members, Pre-Consent)

- 1. Family members will be excluded if they lack English fluency or have other limiting factors that inhibit their ability to use the app (e.g. literacy, blindness, etc).
- 2. Family members will be excluded if they are not directly involved in decision making, are unreachable or unavailable.
- 3. Family members will be excluded if they are <18 years of age.
- 4. Family members will be excluded if they are unable to consent (e.g., dementia, cognitive impairment).
- 5. Prisoners.
- 6. For the RCT only: family members who self-identify as Hispanic and/or self-identify most with a racial group other than White or Black will be excluded.
 - a. Ethnic and racial exclusions do not apply to the ancillary study.

Exclusion Criteria (Patient/Family Dyad Post-Consent)

- 1. Patient dies before T2 is completed.
- 2. Family members will be excluded from the RCT, but not the ancillary study, who have a very low need burden (NEST < 15) after the completion of T1.
- 3. For the primary RCT, participants are also excluded if the randomized physician leaves ICU service or is replaced by a non-participating ICU physician < 2 calendar days after family completes T1.

For Aim 4 RCT (or Aim 3 Ancillary Study) Only:

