Given the nature of the targeted patient population (i.e. those who are mechanically ventilated in an ICU), it is expected that they will not have the capacity to legally give effective consent. As a result, the family member (primary caregiver) and legally authorized representative (LARD) will be asked to consent on their behalf.

For those patients who have decision making capacity (DMC), they will not be excluded from participating. The family member (primary caregiver) of the patient will still be asked to consent and will be the primary responder for the study surveys; however, the patient who has DMC will be asked to consent on their own behalf to allow the study team to collect necessary medical information from their EMR for data analysis instead of the patient's LAR.

Study Interventions

• If not already presented in #4 above, describe study-related treatment or use of an investigational drug or biologic (with dosages), or device, or use of another form of intervention (i.e., either physical procedures or manipulation of the subject or the subject's environment) for research purposes.

The intervention under study is the novel web application known as ICUconnect. The primary purpose of ICUconnect is to develop an accessible, automated, and present application that proactively address needs (i.e. physical, mental, emotional, spiritual, and racial) and improves communication between ICU families, patients and the clinical care team members.

All participants, regardless of study enrollment into to the RCT or ancillary study, will be given access to ICUconnect and asked to complete surveys T1, T2, T3 and T4.

For those patient/family members enrolled into the RCT, they will specifically be assigned to a clinician who has been randomized to one of two study arms: "intervention" or "control". For those patient/family members who are randomized to an "intervention" clinician, the following will occur:

- T1 completed within 24 hours of consent.
 - $^{\circ}$ Assuming a NEST scre of \geq 15, the T1 survey results will be emailed r texted to the randomized clinician.
 - Clinician will review the T1 survey results and then, based n results, conduct a family meeting with the family member. The family meeting is to occur prior to T2.
- T2 completed 3 days after the completion of T1.

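### A family takes the arm of the attending on service at consent; no stated rule fixes the approach date or index attending, and no concealment of arm from recruiters is described, so selective timing is not prevented

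*Protocol*

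**What the plan says.** - **Unit of randomisation** (Protocol, Design & Procedures, Aims 2 and 3): "Randomization occurs at the ICU clinician level versus that of the patient/family level". Under Study Interventions, families in the RCT inherit an arm: "they will specifically be assigned to a clinician who has been randomized to one of two study arms".
- **Which attending counts.** The clinician inclusion criterion (Selection of Subjects) says "Patients' bedside ICU attending physicians on the day of family consent are eligible". The clinician status list (Design & Procedures) defines a consented clinician as "an individual clinician who is on service at the time of the eligible patient/family dyad admission". A third statement, in the Aims 2 and 3 text, gives no date: "Clinicians are identified as eligible if they are the current attending on service for the particular ICU".
- **When families are approached** (same section): "Patient/family dyads will be identified at the time of ICU admission and approached for consent based on meeting study inclusion/exclusion criteria". Selection of Subjects adds a daily review of the medical record.
- **Length of eligibility.** The patient inclusion criteria require at least 24 hours of ventilation in a study ICU. The patient exclusions set the far end: "Patients who are admitted to an ICU at the index hospital >14 days will be ineligible for participation".
- **Rotation of attendings.** A selected clinician "should be scheduled to be on service at least 8 weeks per year". Block length is not given.
- **Primary model** (Data Analysis, Aim 2): terms for T2, T2 by intervention and the listed stratification variables, with family and physician random effects. There is no intervention main effect and no term for ICU day. The SAP names the hierarchical model but adds no covariate for timing and no sensitivity analysis.

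**The concern.** In a cluster trial where participants enter after the cluster's arm is known, randomising the clusters does not by itself make the participants in the two arms comparable. Here the link between family and cluster also depends on a date. If a patient stays eligible across a change of attending, approach on one side of the change gives one clinician, and approach on the other side gives another, perhaps in the other arm. The two statements about which attending counts leave the arm unclear in exactly that case.

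At stake is whether families in the two arms differ in time in ICU at consent, and in whatever prognosis or need goes with it, for reasons unrelated to the intervention. The primary model treats any T1 difference between arms as chance, and nothing in it accounts for when consent took place.

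**Working it through.** **1. The plan's own precision.** Inputs from the power section: SD of change 12, 160 families (80 per arm, 4 per physician), ICC 0.01 to 0.1, two-sided 5%, 80% power.

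SE = 12 × √[(2/80) × (1 + 3 × ICC)]
- ICC 0.01: 12 × √(0.025 × 1.03) = 1.93
- ICC 0.1: 12 × √(0.025 × 1.30) = 2.16

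Detectable difference = (1.96 + 0.84) × SE = 5.39 to 6.06. The plan states 4.0 to 5.0, so its figure is not reproduced from its own inputs. That is a separate matter. The steps below use the SD, sample size and ICC, not the stated detectable difference.

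**2. Eligible span.** With 24 hours of ventilation in the ICU required, the earliest consent is about ICU day 2. The last is day 14. That is at most 13 calendar days, and fewer for patients who are extubated, transferred, die or move to comfort care.

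**3. How often the arm could be known at approach.** Low-scoring families are handled differently by arm after T1 (lost to the study under an intervention clinician, kept for the ancillary study under a control clinician). The team must therefore know the arm by then. If it is known from a clinician's first dyad onward, the share recruited with a knowable arm is 3/4 = 75% (160 families over 40 clinicians, or 240 over 60), and up to 7/8 = 87.5% (240 over 30).

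**4. How often both arms fall within one patient's span.** Block length and the share of attendings enrolled are not stated, so this is illustration only. If the span touches k service blocks and arms are 1:1:
- all attendings enrolled: P = 1 − 2 × 0.5^k
- half enrolled: P = 1 − 2 × 0.75^k + 0.5^k

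Averaging over the starting day in the block, in calendar days:

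| Span (days) | 7-day blocks, all / half enrolled | 14-day blocks, all / half enrolled |
|---|---|---|
| 13 | 68% / 24% | 43% / 11% |
| 5 | 29% / 7% | 14% / 4% |
| 3 | 14% / 4% | 7% / 2% |

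Example (13 days, 7-day blocks, all enrolled): 2 of 7 starting days give k = 2 and 5 of 7 give k = 3, so P = 2/7 × 0.5 + 5/7 × 0.75 = 0.68.

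**5. Effect of a bias on the test.** Type I error = P(|Z + bias/SE| > 1.96).

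| Assumed bias (NEST units) | SE 1.93 | SE 2.16 |
|---|---|---|
| 1 | 8.1% | 7.5% |
| 2 | 18.0% | 15.2% |

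**6. What such a bias would take.** If a share s of families could fall in either arm, all were sorted, and those placed in one arm had an expected change d units better than those placed in the other, the bias is s × d. At s = 29% (5-day span, 7-day blocks, all enrolled), 1 unit needs d = 1/0.29 ≈ 3.5 and 2 units need d ≈ 7. At s = 14%, 1 unit needs d ≈ 7. Partial sorting needs more.

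**The case against.** Several points on the other side are sound.

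- A reader might infer that allocation works by calendar date. It does not. Clinicians are randomised using gender, experience and discipline, and the date only decides which randomised clinician a family falls under.
- A reader might infer that staff can pick any day up to day 14. The documents do not say so. Dyads are identified at ICU admission, screening is daily, the clinical team is asked whether the moment is suitable, the family must be reachable, and same-day extubation leaves 8 hours. Day 14 is a cap, not a schedule. What remains is that no rule requires approach at first eligibility or in consecutive order, and those same constraints can delay consent past a change of attending.
- A reader might infer that most families could be steered. That needs nearly the full span and nearly every attending in the trial. The ancillary study takes families whose attending is not in the RCT, so full participation is doubtful.
- Steering requires knowing the arm. If whoever sets the date does not know it, variation in timing should be alike in both arms and cause no bias. Concealment is therefore part of the remedy.
- The two statements about the attending define a clinician's eligibility and a clinician's status. Neither is written as the rule mapping a family to an arm. But no other passage supplies that rule, so the ambiguity stands.
- Nothing in the documents shows that NEST change varies with ICU day, or that anyone times approaches by arm.

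The eligibility workflow that the Protocol refers to is not reproduced in the text reviewed. If it fixes an approach rule, that part of the point falls away.

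**Conclusion.** The point holds in a limited form. Families enter after their clinician is randomised, the Protocol gives two different days for identifying that clinician, and the text fixes neither the approach date nor the index attending. Neither document describes concealing the arm from recruiters. Selective timing is not prevented. There is no evidence that it was intended or took place.

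If timing led to a difference in expected T1-to-T2 change, it would enter b2, and the planned analyses would not reveal it. An assumed bias of 1 NEST unit (1/12 = 0.08 SD) takes the error rate from 5% to about 7.5–8%, and 2 units to about 15–18%. Both bias sizes are illustrative. They rest on the plan's SD, 160 families and its ICC range, and the share of families who could fall in either arm turns on rota length and attending participation, which are not stated. The point justifies a wording change and a few extra tabulations. It does not justify discounting the trial's result.

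**What to change.** **Protocol.** Reconcile the Aims 2 and 3 text, the clinician status definition and the clinician inclusion criterion to one rule. The index attending is the one on service at the first daily record review at which the patient meets the criteria, entered in the screening log before any contact with the family. Approach eligible families consecutively and promptly from that date. Where feasible, keep whoever sets the approach date unaware of the arm until T1 is complete. The index rule is not enough alone: staff who know the arm could still delay or skip an approach, which would turn switching of arms into arm-dependent exclusion.

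Cost: wording and one log field. Some dyads whose attending changes before consent would be lost to the RCT; count these losses by arm. The existing exclusion for physicians who leave service within 2 calendar days of T1 already accepts losses of this kind.

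**SAP.** By arm, report the numbers eligible, approached and consented, and the days from first eligibility to consent. Add a Hypothesis 2a analysis adjusted for ICU day at consent, and a sensitivity analysis restricted to dyads consented under the index attending.

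Cost: a little analysis work using medical-record and consent dates. The SAP is written in the past tense, so the Protocol change may come too late for families already enrolled. The SAP change remains possible after enrolment is complete.
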